5.4 Definition of Visit Windows

All available values will be used in the statistical analysis independent of whether they are within or outside the pre-defined visit windows. No specific visit windows will be defined for the statistical analysis.

5.5 Changes from the Planned Statistical Analysis in Protocol

The following changes from the planned statistical analysis in the protocol were made:

- In some instances, techniques will be used to adjust for missing data.
- In addition to the Full Analysis Set, a Per Protocol Analysis Set and a Pharmacokinetic Full Analysis Set were added.
- Pharmacokinetic parameters will be calculated using non-compartmental analysis (NCA), rather than a model combining data from this and previous studies, due to the lack of a suitable model.
- In order to determine the incremental recovery (IR) over time and see if antibodies have affected the recovery following long-term exposure, it is important to compare the end of study IR with the baseline IR. Therefore the IR will be summarized for baseline and end of study only rather than for all available time points.

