### 7.2 Study Objectives

The objectives of this study are to:

- Further evaluate safety of BAX326 in terms of IP-related AEs as well as clinically significant changes in routine laboratory parameters (hematology/clinical chemistry) and vital signs
- Further evaluate the hemostatic efficacy of BAX326 in the prevention and routine prophylaxis of acute bleeding episodes using various dose regimens
- Further evaluate the hemostatic efficacy of BAX326 in the management of acute bleeding episodes
- Further evaluate the immunogenicity of BAX326 for up to 100 EDs to BAX326x
- Monitor IR of BAX326 over time
- Evaluate changes in health-related quality of life (HR QoL), Patient Activity Level and health resource use
- Exploratory: To correlate pre-infusion TGA parameters with pre-infusion FIX levels and spontaneous breakthrough bleeds in a subset of subjects receiving twice weekly standard or modified prophylaxis including PK tailored prophylaxis.

---

x Subjects who have participated in BAX326 Pivotal Study 250901 or Pediatric Study 251101, and in BAX326 Continuation Study 251001 will have accumulated a total of up to approximately 100 EDs in both studies.

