Subsequent study visits will be performed every 3 monthsxiii  $\pm 1$  week after study start (ie, screening visit) until study completion; additional visits may occur if clinically indicated. Hemostatic efficacy and the occurrence of AEs will be evaluated based on the review of the patient diary. Testing for IR, inhibitory and binding antibodies, clinical chemistry and hematology will be performed at the same time points. In addition to the time points mentioned above, the presence of inhibitory and total binding antibodies to FIX will be tested whenever clinically indicated, e.g. on lack of response to treatment, or if severe allergic reactions occur, such as anaphylaxis.

At the same time points health resource use will also be determined. Every other visit (ie, every 6 months  $\pm 1$  week), data on HR QoL will be collected.

For the hemostatic efficacy assessment the following information will be recorded by the subject or subject's legal representative or by authorized study site personnel in the patient diary: bleeding location, type, severity, onset date and time, infusion date and time, analgesics required, and clinical efficacy according to the rating scale.

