#### **8.2 Duration of Study Period(s) and Subject Participation**

The total period of study participation per study subject will vary and can be up to a maximum of 68 months, depending on the date of subject enrollment and the product licensure in the subject's respective country, and whether the subject has accumulated a total of 100 EDs to BAX326 during the course of the Pivotal (# 250901) or Pediatric (# 251101) Study and the Continuation Study (# 251001), whichever occurs last, but will not last beyond December 31, 2016.

For newly recruited subjects, the study participation will be up to approximately 100 EDs, but not beyond December 31, 2016. However, a limited number of patients may not have reached 100 EDs by that date and they will continue until they have reached approximately 100 EDs.

Subjects will participate in this continuation study until BAX326 is licensed in their respective countries, and they have accumulated a total of at least 100 EDs to BAX326, however, no later than December 31, 2016.

The duration of the study will be approximately 68 months depending on the date of licensure in subjects' countries.

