#### **14.3.2.2 Pharmacokinetics**

PK parameters will be calculated for all subjects planned to receive a PK-tailored treatment regimen using a non-linear mixed effects model approach.

The available PK data (FIX activity levels) from pivotal study 250901, pediatric study 251101 and surgery study 251002 will be utilized together in the model and strengthen the estimation of the full PK curve even if only sparse samples are available for an individual.

The following PK parameters for FIX will be reported using descriptive statistics: AUC0-∞ (area under the plasma concentration/time curve from time 0 to infinity), IR, T1/2 (elimination phase half-life), MRT (mean residence time), CL (clearance), Vss (Volume of distribution at steady state). Incremental recovery (IR) will be determined as the changes in FIX activity level from pre-infusion to 30 ± 5 minute post-infusion, divided by dose, and reported as (IU/dL)/(IU/kg). FIX activity levels at pre-infusion reported as < 1% will be used as 0.5% for the calculation of IR.

Incremental recovery of FIX will be summarized by visit and displayed graphically over time for each subject. Also the change from baseline (at screening visit) will be described using summary statistics. As the maximum dose can be 120 IU/kg any doses higher than 120 IU/kg are not allowed and therefore frequencies requiring a higher are excluded.

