1.1 Study Objectives

The objectives of this study are:

- To further evaluate safety of BAX326 in terms of investigational product (IP) related adverse events (AEs) as well as clinically significant changes in routine laboratory parameters (hematology/clinical chemistry) and vital signs.
- To further evaluate the hemostatic efficacy of BAX326 in the prevention and routine prophylaxis of acute bleeding episodes using various dose regimens.
- To further evaluate the hemostatic efficacy of BAX326 in the management of acute bleeding episodes.
- To further evaluate the immunogenicity of BAX326 for up to 100 exposure days (EDs) to BAX326.
- To monitor incremental recovery (IR) of BAX326 over time.
- To evaluate changes in health-related quality of life (HR QoL), Patient Activity Level and health resource use.
- Exploratory: To correlate pre-infusion thrombin generation assay (TGA) parameters with pre-infusion FIX levels and spontaneous breakthrough bleeds in a subset of subjects receiving twice weekly standard or modified prophylaxis including pharmacokinetic (PK) tailored prophylaxis.

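### Incremental recovery is measured every 3 months, but the SAP tables only baseline and end of study, so no group-level summary of the intermediate visits is planned and the FAS profile plot is not clearly kept

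*SAP*

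**What the plan says.** Both documents carry the same objective: "Monitor IR of BAX326 over time" (Protocol 7.2) and "To monitor incremental recovery (IR) of BAX326 over time" (SAP 1.1). IR over time is also a secondary outcome measure (Protocol 8.3.2.3, SAP 3.2.3).

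The measurement schedule is dense. For transitioning subjects, Protocol 8.1.1 sets 3-monthly visits and adds: "Testing for IR, inhibitory and binding antibodies, clinical chemistry and hematology will be performed at the same time points". Protocol 11.1.1 and 11.1.3 confirm this and include a value at termination or completion. Newly recruited subjects also have IR at the first exposure day (ED1) and at Week 4. Participation "can be up to a maximum of 68 months" (Protocol 8.2).

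On analysis, Protocol 14.3.2.2 says: "Incremental recovery of FIX will be summarized by visit and displayed graphically over time for each subject". It plans change from baseline in addition.

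SAP 5.5 lists a change from that plan. It argues that "it is important to compare the end of study IR with the baseline IR" and concludes: "Therefore the IR will be summarized for baseline and end of study only rather than for all available time points". SAP 9.1 implements this on the FAS with tables for baseline, end of study and change, and keeps a by-subject listing of IR. The revision history records the restriction under version 2.0 (27 Sep 2017). A sentence promising a graph of IR over time for each subject remains in SAP 9.2, the abbreviated-PK section.

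**The concern.** The objective concerns the course of recovery over long exposure. The planned tables describe its two ends and nothing between them. The reason given in SAP 5.5 supports keeping the baseline-to-end comparison, which the protocol already had. It does not explain why the by-visit summary had to be removed to make room for it.

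At stake is a fall in recovery that later resolves. SAP 5.5 frames its interest as whether antibodies have affected recovery. Under Protocol 12.7.1.2, a subject with binding antibodies at a titer of 1:80 or more stays in the study. If that subject's recovery dipped and came back, both tabled values could look normal.

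**Working it through.** No sample size, power or error rate attaches to this point, and the plan states no figure to reproduce. The check has two parts: how many scheduled IR values reach the tables, and which outputs still cover the rest.

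**1. Count of regular IR time points**

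Inputs: visits every 3 months, with months of 30 days (Protocol 8.1.1 footnote); maximum duration 68 months (Protocol 8.2); IR visits from Protocol 11.1.1 and 11.1.3. Optional additional visits, and the extra Week 4 visit for PK-tailored Cohort 1 subjects, are not counted.

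Cohort 1, follow-up of m months:
- 3-monthly visits before completion = ceil(m/3) − 1
- total = that number + 2 (screening and completion)

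| m (months) | Intermediate visits | Total | Share in the tables |
|---|---|---|---|
| 12 | 4 − 1 = 3 | 5 | 2/5 = 40% |
| 24 | 8 − 1 = 7 | 9 | 2/9 = 22% |
| 48 | 16 − 1 = 15 | 17 | 2/17 = 12% |
| 68 | 23 − 1 = 22 | 24 | 2/24 = 8% |

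Cohort 2: "For newly recruited subjects, the study participation will be up to approximately 100 EDs". The documents do not fix an infusion frequency for every subject, so the conversion of 100 exposure days (EDs) to months is an assumption, shown over a range of k infusions per week:
- months = (100/k) × 7/30
- total = ceil(months/3) − 1 + 3 (ED1, Week 4 and completion)

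| k per week (assumed) | Months | Total | Share in the tables |
|---|---|---|---|
| 1 | 23.3 | 8 − 1 + 3 = 10 | 2/10 = 20% |
| 2 | 11.7 | 4 − 1 + 3 = 6 | 2/6 = 33% |
| 3 | 7.8 | 3 − 1 + 3 = 5 | 2/5 = 40% |

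**2. What covers the intermediate visits**

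- *Summary tables (SAP 9.1, FAS):* expressly baseline, end of study and change. Intermediate visits are out.
- *By-subject listing (SAP 9.1, FAS):* kept, but the visits are not stated.
- *Per-subject graph over time (SAP 9.2):* kept, but SAP 9.2 assigns its PK-parameter analysis to the PKFAS. SAP 4.3 defines that set as FAS subjects with an abbreviated PK study, and SAP 5 notes that these were all adults. Read by its placement, the graph leaves out every child and every adult without an abbreviated PK study.
- *Antibody table (SAP 8.2):* counts subjects with antibodies but does not link them to IR.

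So no summary statistic includes an intermediate visit, and no graph of IR over time is clearly planned for the FAS.

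**The case against.** The strongest defence has four parts.

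- **The change is open and coherent.** SAP 5.5 declares it with a reason, and SAP 9.1 follows it. In an uncontrolled, descriptive study, change from baseline to end is a sensible summary of lasting loss. This stands.
- **Individual courses are still reported.** Nothing limits the listing to two visits, and SAP 5.2 sends even unscheduled measurements to listings. An abbreviated PK study yields a single IR, so a graph of IR over time in SAP 9.2 may simply be the protocol's longitudinal plot in the wrong place. This is plausible, but the text does not settle it, and clarifying it costs a sentence.
- **Inhibitors are handled elsewhere.** A reader might infer that a fall caused by an inhibitor would be missed. The documents do not support that. Antibodies are tested every 3 months and their occurrence is tabled. A confirmed inhibitor of 0.6 BU or more leads to discontinuation (Protocol 9.3, 12.7.1.2), and the termination visit includes an IR. For a subject who attends it, the end-of-study value follows the inhibitor. The gap is mainly non-inhibitory binding antibodies and unconfirmed findings.
- **By-visit means have limits.** Averaging would mask one subject's temporary fall, and participation depends on licensure and exposure days, so late visits hold a shrinking, selected group. Both points stand. They make the individual profiles the more informative output and mean that n must be shown at each visit.

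**Conclusion.** The concern holds in a limited form. Against the protocol's own plan, no group-level summary of the intermediate IR visits remains, and the scope of the two surviving individual-level outputs is unclear. At the 68-month ceiling, 2 of up to 24 regular values per Cohort 1 subject enter the tables. For shorter follow-up the share is larger: 2 of 9 at 24 months and 2 of 5 at 12 months. For Cohort 2 at an assumed two infusions per week it is 2 of 6. These counts assume that every scheduled visit is attended.

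A reader might go further and conclude that the objective is left unanswered or that mid-study falls are concealed. The documents do not support either conclusion. The departure is disclosed, lasting loss is assessed, and a by-subject listing on the FAS and a per-subject graph are both retained. What is missing is narrower: a temporary fall would appear in no summary statistic and in no graph clearly planned for the FAS.

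**What to change.** Keep the baseline-to-end table. In SAP 9.1:

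- Restore the protocol's by-visit IR summary on the FAS, showing n at each visit with a note that late visits hold fewer, selected subjects.
- Move the per-subject plot of IR over time from SAP 9.2 to SAP 9.1 and specify the FAS.
- State that the by-subject listing covers all IR visits.
- Optionally, add each subject's lowest IR and largest fall from baseline. These capture a temporary individual fall that a visit mean would not.

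Present these for subjects under 12 and those 12 or older. The opening of SAP 9 already calls for that split, while SAP 5 exempts pharmacokinetic analyses from it because only adults had an abbreviated PK study. The two statements should be reconciled so that IR over time, a FAS analysis, keeps the split.

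The cost is one table and one figure from data already collected, plus a few sentences in the SAP.

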6. STUDY SUBJECTS

6.1 Disposition of Subjects

The number (%) of subjects who were enrolled and treated will be summarized overall, by cohort and by treatment regimen. The number (%) of subjects who completed the study, or discontinued for any reason will also be summarized overall, by cohort and by treatment regimen. The details of the discontinued subjects will be presented in a listing with the reason for discontinuation. Subject disposition will also be presented by study site.

The number of subjects in each specific data set will be summarized by treatment regimen as well as for all treatment regimens together. Details of subjects excluded from any data set will be listed.

A disposition flowchart will be included.

A by-subject listing of lot numbers used will be provided.

6.2 Demographic and Baseline Characteristics

Demographic data will be summarized descriptively and listed by treatment regimen as well as for all treatment regimens together:

- Age at Screening
- Age at Screening of Parent Protocol (applicable only for transitioning subjects)
- Gender
- Ethnicity (for US only)
- Race
- Height [cm] at Screening
- Weight [kg] at Screening
- Body mass index (BMI) [kg/m^2] at Screening.

Demographic variables will be summarized for the FAS, the PPAS and the PKFAS.

6.3 Medical History

Medical history will be listed for subjects in the FAS.

6.4 Prior Therapies and Medication

Prior therapies and medication will be listed for subjects in the FAS.

6.5 Concomitant Medications

Concomitant medications, non-drug therapies and hemostatic products other than BAX326 will be listed for subjects in the FAS.

6.6 Measurements of Treatment Compliance

Treatment compliance for subjects on prophylaxis will be summarized on the FAS and a subject-level listing will also be provided.

The compliance measures regarding frequencies are:

- Standard prophylaxis: number of prophylaxis infusions within 2.5-4.5 days of previous infusion / total number of standard prophylaxis infusions
- PK-tailored prophylaxis: number of PK-tailored prophylaxis infusions within 6-8 days of previous infusion / total number of PK-tailored prophylaxis infusions

The compliance measures regarding dose limits are:

- Standard prophylaxis:
 - Subjects \geq 12 years: number of prophylaxis infusions within 40-75 IU/kg / total number of standard prophylaxis infusions
 - Subjects $<$ 12 years: number of prophylaxis infusions within 40-80 IU/kg / total number of standard prophylaxis infusions
- Modified prophylaxis: number of modified prophylaxis infusions \leq 100 IU/kg / total number of modified prophylaxis infusions
- PK-tailored prophylaxis: number of PK-tailored prophylaxis infusions \leq 120 IU/kg / total number of PK-tailored prophylaxis infusions

The compliance measures regarding prescribed doses are:

- Standard prophylaxis: number of prophylaxis infusions within 10% of the prescribed dose / total number of standard prophylaxis infusions
- Modified prophylaxis: number of modified prophylaxis infusions within 10% of the prescribed dose / total number of modified prophylaxis infusions
- PK-tailored prophylaxis: number of PK-tailored prophylaxis infusions within 10% of the prescribed dose / total number of PK-tailored prophylaxis infusions

The compliance measures regarding dose limits and prescribed doses are:

- Standard prophylaxis:
 - Subjects \geq 12 years: number of prophylaxis infusions within 40-75 IU/kg and within 10% of the prescribed dose / total number of standard prophylaxis infusions
 - Subjects $<$ 12 years: number of prophylaxis infusions within 40-80 IU/kg and within 10% of the prescribed dose / total number of standard prophylaxis infusions
- Modified prophylaxis: number of modified prophylaxis infusions \leq 100 IU/kg and within 10% of the prescribed dose / total number of modified prophylaxis infusions
- PK-tailored prophylaxis: number of PK-tailored prophylaxis infusions \leq 120 IU/kg and within 10% of the prescribed dose / total number of PK-tailored prophylaxis infusions

Note that the regimen, dose and/or frequency of dosing may change during the prophylaxis observation period.

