## **6.5 Evaluation of Anticipated Risks and Benefits of the Investigational Product(s) to Human Subjects**

Clinical data with BAX326 have been generated in the completed Phase 1/3 pivotal study (Study 250901), the completed Phase 2/3 study 251101 in pediatric PTPs < 12 years of age and the completed Phase 3 surgery study 251002. Additional data are collected in the present continuation study (Study 251001) to further generate data on efficacy, safety and immunogenicity until subjects have accumulated a total of at least 100 EDs or until the product is licensed in their respective country, however no later than December 31, 2016. A limited number of patients may not have reached 100 EDs by that date and they will continue until they have reached approximately 100 EDs. Subjects who have completed the BAX326 pivotal or BAX326 pediatric study can be transitioned into this study.

BAX326 was shown to be efficacious for routine prophylactic treatment and control of bleeding episodes (on-demand treatment) in PTPs across all age groups with hemophilia B. BAX326 was also found to be efficacious in the surgical hemostasis of 38 surgeries, of which 21 were major (14 major orthopedic surgeries) and 17 were minor surgeries.

A total of 4 clinical studies with a total of 99 unique subjects treated with BAX326 in one or more of the 4 studies have been included in an integrated analysis of safety (ISS) with a data cut-off date of 14 June 2013: 73 subjects treated either prophylactically (n=59) or on-demand (n=14) with BAX326 in the completed pivotal study 250901, 23 subjects treated prophylactically with BAX326 in the completed pediatric study 251101, 30 subjects treated in the surgery study 251002, which was ongoing at the time of the ISS but has in the meantime been completedvi, as well as available safety data from the ongoing continuation study 251001 (n=82).vii The 99 unique subjects in these 4 studies received at least one infusion of BAX326, with a total consumption of 50,756,155 IU of BAX326 in 14,018 infusions. The majority of infusions were administered for prophylaxis (40,172,963 IU administered in 11,504 infusions). Exposure per subject was a median of 156 EDs (range: 8 to 316 exposure days), with a median of 163 infusions per subject (range: 8 to 327 infusions) and a median consumption of BAX326 per subject of 8201.8 IU/kg (range: 376 to 22,705 IU/kg).

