**Table 21.1-1**  
**Flow Diagram of Required Procedures for Baxalta Clinical Study 251001**

**6. Study Visits Every 3 Months ± 1 Week Following Screening in Subjects Transitioning from BAX326 Pivotal or BAX326 Pediatric Study; Study Visits Every 3 Months ± 1 Week Following ED1 for Newly Recruited Subjects**

Each visit must be arranged so that there is a wash-out period of at least 5 days (120 hours), preferably 7 days, from the latest dose of BAX326. The subject must not be actively bleeding. For subjects switching back to this study from the surgery studyxxiv, the respective visit window may be extended from ± 1 week to ± 2 weeks.

At each study visit the following procedures will be carried out:

Prior to the recovery assessment:

- Review and discuss subject diary
- Review and discuss the number of spontaneous bleeding episodes
- Review number of EDs to BAX326
- Record AEs
- Concomitant medication and non-drug therapy use
- HR QoL including Patient Activity Level pre- or post-infusion of BAX326 – every second visit (every 6 months ±1 week)
- Collection of Health Resource Utilization items
- Physical examination
- Occurrence of target joints
- Blood draws for:
  - a) Immunology (pre-infusion of IP)
  - b) Hematology and clinical chemistry
- Urine sample for urinalysis
- Vital signs within 15 minutes of start of infusion
- CD4 count will be assessed **once a year**.
- **Assessment of FIX Recovery (and TGA parameters, if applicable)**
  - a) Pre-infusion blood draw for FIX activity (and TGA parameters, if applicable) within 0.5 h of start of infusion
  - b) Infusion of  $75 \pm 5$  IU/kg BAX326 at a rate not to exceed 10 mL/min
  - c) Post-infusion blood draw for FIX activity (and TGA parameters, if applicable) at  $30 \pm 5$  minutes
  - d) Vital signs at  $30 \pm 5$  minutes and  $2 h \pm 10$  minutes following completion of the infusion

xxiv Surgery Study 251002 was completed in May 2014. Thirty unique subjects underwent 38 surgeries.

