2.1 Cohort 1: Subjects Transitioning from BAX326 Pivotal or BAX326 Pediatric Study

All subjects who completed Baxter Pivotal Study 250901 or Pediatric Study 251101 have an option to enroll in the continuation study (Cohort 1). The treatment regimen with BAX326 will be at the discretion of the investigator and will consist of one of the following treatment options:

- Standard prophylaxis with twice weekly prophylactic infusions of 50 IU/kg (range of 40-60 IU/kg, which may be increased to 75 IU/kg, in subjects \geq 12 years of age; range of 40-80 IU/kg in pediatric subjects < 12 years), or
- modified prophylaxis determined by the investigator. The dose can be increased up to 100 IU/kg, if applicable; or
- PK-tailored prophylaxis based on subject's individual pharmacokinetics (PK). The maximum dose is 120 IU/kg; or
- on-demand treatment.

The screening visit for the continuation study will be performed on the same day as the end of study/termination visit of the pivotal or pediatric study in order to ensure continuity of BAX326 therapy. Subjects can be given the Informed Consent Form prior to the termination visit of Pivotal Study 250901 or Pediatric Study 251101 to ensure ample time for reviewing and considering the participation in the continuation study 251001. Subjects will be supplied with IP for a maximum of 5 weeks at the screening visit. The subject will then return to the study site no later than 4 ± 1 weeks to review the results of the screening visit (including results from termination visits for Study 250901 or 251101), and confirm their eligibility for continued participation.

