7.2.2 Prophylaxis: Annualized Bleed Rate

The ABR will be calculated as follows:

$$\frac{\text{Number of bleeding episodes}}{\text{Observed treatment period in days}} * 365.25.$$

The ABR will be listed and summarized only for subjects who have adequate treatment time for bleeding rate assessment. For subjects on prophylaxis, a subject is considered to have an adequate treatment time for bleeding rate assessment if the observation period with BAX326 in this study within the respective treatment regimen was a minimum of 3 months (treatment period for surgery and bleeding period are not counted).

The observation period for prophylactic treatment is considered as the time between the first and the last prophylactic infusions. For transitioning subjects, infusions prior to eligibility assessment will count in case the treatment regimen is the same as the regimen the subject receives after eligibility is confirmed. The treatment period for surgery as well as the bleeding period will be excluded from the calculation of observation period in the calculation.

Additionally, the ABR will also be calculated for subjects with on-demand treatment. The observation period for on-demand treatment is considered as the time between the date of eligibility (or the date of switching to on-demand for subjects who were on prophylaxis before) and the end of observation period.

These tables will be created by treatment regimen.

ABR will be also presented by bleeding site (joint/non-joint), cause (spontaneous/injury), severity (minor, moderate, major, and life/limb-threatening), presence of target joints and FIX activity levels at screening. These subgroup analyses will be performed on the FAS only.

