13. REVISION HISTORY

Version	Issue Date	Summary of Changes
1.0	26 Jul 2017	New Document
2.0	27 Sep 2017	
Section 6.6: Updated denominator for clarification and deleted compliance assessment regarding frequencies for modified prophylaxis since definition how data should have been captured was given insufficiently.
 
Section 9.1 and 11.2: IR and TGA will be summarized for baseline and end of study only rather than for all available time points.
 
Minor updates for clarification throughout the whole document.

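### Frequency compliance in SAP 6.6 divides by infusions given, not infusions due, so an unrecorded break followed by resumption lowers the score by only about 1/n, whatever its length

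*SAP*

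**What the plan says.** SAP 6.6 defines two frequency measures. For standard prophylaxis it is "number of prophylaxis infusions within 2.5-4.5 days of previous infusion / total number of standard prophylaxis infusions". For PK-tailored prophylaxis it is "number of PK-tailored prophylaxis infusions within 6-8 days of previous infusion / total number of PK-tailored prophylaxis infusions". The remaining measures in that section concern dose, and they too are divided by infusions given. Neither document defines a count of scheduled or due infusions, a longest-gap measure or a compliance threshold.

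Modified prophylaxis has no frequency measure. The SAP 13 entry for version 2.0 reads "Updated denominator for clarification and deleted compliance assessment regarding frequencies for modified prophylaxis" and gives as the reason that the way the data should have been captured was not defined well enough.

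The prophylaxis ABR in SAP 7.2.2 uses a related time base: "The observation period for prophylactic treatment is considered as the time between the first and the last prophylactic infusions". Only surgery and bleeding periods are taken out of it.

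**The concern.** A compliance table is where a reader looks to see whether the prophylaxis ABR describes the regimen as prescribed. With infusions given as denominator, the ratio measures how regular the intervals between actual infusions were. It does not measure how much of the prescribed prophylaxis was taken.

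While a subject is off treatment nothing is added to either half of the ratio, and only the restart infusion falls outside the window. The ABR does keep that time, because an untreated gap between the first and last prophylactic infusion is part of the observation period and its bleeds are counted. A reader would then see bleeds under prophylaxis next to a high compliance figure, and could put down to the product what belongs to omitted doses.

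**Working it through.** The documents give no compliance figure, so there is nothing to reproduce. The check asks what the defined ratio returns for a known pattern of infusions.

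**Inputs**
- Regimen: "Standard prophylaxis with twice weekly prophylactic infusions of 50 IU/kg" (SAP 2.1), taken as alternating 3- and 4-day intervals. Over 12 months this is 105 infusions: one on day 0, then 365.25/3.5, about 104.
- Window: 2.5-4.5 days (SAP 6.6).
- Visit wash-out: "Each visit must be arranged so that there is a wash-out period of at least 5 days (120 hours), preferably 7 days" (Protocol Table 21.1-1, item 6). Such an infusion is outside the window by design. The SAP does not say whether it counts, so both readings are shown.
- Guide to n: subjects stay until "they have accumulated a total of at least 100 EDs to BAX326" (Protocol 8.2, with a calendar limit), and for the four studies together "Exposure per subject was a median of 156 EDs (range: 8 to 316 exposure days" (Protocol 6.5).
- Assumption, not in the documents: one unrecorded break of 1, 3 or 6 months, then resumption, with all other infusions on time.

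**Formula, wash-outs not counted.** With n infusions given and one break, the score is (n-1)/n if the subject's first infusion is credited. It is (n-2)/n if that infusion fails for want of a predecessor. The length of the break enters only through n.

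| Break in 12 months | Given | Score, first credited | Score, first not credited | Given/due |
|---|---|---|---|---|
| 1 month | 96 | 95/96 = 99.0% | 94/96 = 97.9% | 96/105 = 91.4% |
| 3 months | 79 | 78/79 = 98.7% | 77/79 = 97.5% | 79/105 = 75.2% |
| 6 months | 53 | 52/53 = 98.1% | 51/53 = 96.2% | 53/105 = 50.5% |

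With n = 100 given the score is 98.0-99.0%, with n = 156 it is 98.7-99.4%, and with n = 26 it is 92.3-96.2%.

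**Wash-outs counted.** Visits fall every 90 days, each infusion there follows 5 or 7 days without product, and visit infusions are also given during the break.

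| Break in 12 months | Wash-out | Given | Out of window | Score, first credited | Score, first not credited | Given/due |
|---|---|---|---|---|---|---|
| None | 5 days | 102 | 4 | 98/102 = 96.1% | 97/102 = 95.1% | 100% |
| None | 7 days | 98 | 4 | 94/98 = 95.9% | 93/98 = 94.9% | 100% |
| 3 months | 5 days | 78 | 5 | 73/78 = 93.6% | 72/78 = 92.3% | 78/102 = 76.5% |
| 3 months | 7 days | 75 | 5 | 70/75 = 93.3% | 69/75 = 92.0% | 75/98 = 76.5% |
| 6 months | 5 days | 53 | 5 | 48/53 = 90.6% | 47/53 = 88.7% | 53/102 = 52.0% |
| 6 months | 7 days | 52 | 4 | 48/52 = 92.3% | 47/52 = 90.4% | 52/98 = 53.1% |

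The break adds at most one out-of-window infusion to the four that the visits produce anyway. The score falls by somewhat more than 1/n because those visit infusions become a larger share of a smaller n. The drop from the fully adherent score is 2.5-2.9 points for 3 months and 3.6-6.4 points for 6 months.

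**PK-tailored, weekly infusions, wash-outs not counted.** One year less 3 months leaves 39 of 52 infusions (75%) and scores 94.9-97.4%. Less 6 months leaves 26 of 52 (50%) and scores 92.3-96.2%.

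**Isolated misses.** Ten separate misses out of 104 due leave 94 given, of which 10 are out of window: 84/94 = 89.4%, against 94/104 = 90.4% given/due. The ratio works for isolated misses and fails for runs of them.

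**The case against.** The best defence is that the plan has other safeguards and that the scenario is assumed. Nothing in the documents shows breaks of 3 to 6 months. Product is dispensed for at most 3 months at a time, the investigator must review adherence and the diary at each visit (Protocol 10.5), and regimen changes are recorded with reasons (Protocol 8.6.3.1). SAP 5 moves data to the new regimen once a change is recorded. SAP 7.2.3 reports infusions per month and year by regimen, SAP 8.3 exposure days and SAP 6.7 protocol deviations. Compliance feeds no threshold, per-protocol criterion or ABR calculation, the efficacy analysis is descriptive and secondary, and the distortion works against the product.

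Much of this stands and limits the point to unrecorded breaks that end in resumption. It does not remove it, because detecting unrecorded lapses is what a compliance measure is for. The figures in SAP 7.2.3 are not compared with the prescribed frequency and are not limited to prophylactic infusions, so bleed treatments during a gap can mask omissions.

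A reader might infer three stronger things that the documents do not support:
- That anyone who stops for months still scores 98-99%. This requires roughly 50 to 100 or more infusions given, every other infusion on time, the first infusion credited and visit infusions not counted as failures. With wash-outs counted, not even a fully adherent subject reaches it.
- That a break always costs exactly one infusion. A permanent stop costs none, and the ABR period ends there too. A break that spans visits can contain more than one out-of-window infusion.
- That no planned output shows the shortfall. Infusions per month and year show it in part.

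**Conclusion.** The concern holds in limited form. The frequency measures for standard and PK-tailored prophylaxis cannot separate near-full adherence from months without prophylaxis. In the one-year twice-weekly example, a break that removes about a quarter to a half of due infusions leaves a score of about 96-99% with visit wash-outs not counted, or about 89-94% with them counted against 95-96% for full adherence.

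The denominator fault follows from the SAP's wording alone. Its size rests on the assumed single, unrecorded break with all other infusions on time. How often such breaks happened cannot be known from the documents. The SAP should be corrected because the table would mislead a reader of the prophylaxis ABR, but the primary outcome (related adverse events) is not affected.

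**What to change.** In SAP 6.6:

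1. **Standard and PK-tailored prophylaxis.** Add prophylactic infusions given divided by infusions due. Due = eligible observation days x prescribed infusions per week / 7, using the prescribed frequency in force at the time and removing visit wash-outs, surgery and bleeding periods.
2. **Same two regimens.** Add the number and total days of gaps outside scheduled wash-outs: longer than 7 days for standard prophylaxis, and longer than 8 days for PK-tailored prophylaxis given its 6-8 day window.
3. **Existing ratio.** Keep it, label it interval adherence, and state how a subject's first infusion and the visit infusions are counted.
4. **Modified prophylaxis.** Report only actual prophylactic infusions per week and gap days, which need infusion dates alone. A given/due ratio is not shown to be feasible there, because the SAP's own revision history says that the capture of frequency data was insufficiently defined.

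The inputs are the infusion dates and reasons in the diary (Protocol 10.5) and the regimen changes in the eCRF (Protocol 8.6.3.1). The cost is SAP wording and a little extra programming, and reported compliance will be lower. No treatment rule changes.
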